Intake survey: After consent but prior to HIV testing, we will conduct a baseline survey. This method of obtaining consent prior to HIV testing has been effective in prior research in Nakivale as it allows for baseline data collection before individuals learn of a new HIV diagnosis which could alter their survey answers. This will include collection of contact information, demographic information, physical assessment (height, weight, blood pressure), migration patterns (e.g. country of origin, years in Nakivale, recent time away from Nakivale), HIV testing history, perceived stigma, screening for mental disorders (PTSD, depression, anxiety), and assessment of social support (see Appendix I: "Survey"- Runyankore, Kinyarwanda, Kiswahili, English). The purpose of the intake survey is to understand if any of these factors are associated with uptake of or engagement in the Early CCLAD groups as a means to enhance engagement in care in the future. Like the consent process, the survey will be available in 4 languages: Runyankore, Kinyarwanda, Kiswahili or English, and will be read aloud to participants with responses entered directly into a passcode-protected electronic tablet.

Early Community Client-Led ART Delivery (Early CCLAD) intervention: Willing participants newly diagnosed with HIV will be placed into a Community Client-Led ART Delivery group. The goal will be to place participants into groups within the first month of diagnosis. We will attempt to ask participants what their ideal group would look like (i.e. sex of other group members, proximity of house to other group members, country of origin of other group members, size of group), and we will work to place participants in groups that they anticipate will work best for them. We anticipate groups will range in size from 3-12 participants. As enrollment permits, we will invite participants to indicate their preferred group size and group characteristics (sex, age, country of origin of participants). We will not initiate a participant into group after 90 days of diagnosis. To facilitate linkage to the Early CCLAD group, clients will be linked to an expert client peer navigator. The

expert client peer navigators will be tasked with supporting the Early CCLAD intervention groups and helping provide psychosocial support to newly diagnosed individuals and helping them seamlessly integrate with their group.

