Monthly “Early CCLAD” meetings: The “Early CCLAD” intervention will require monthly group meetings. This is intentionally more frequent than is suggested in the Ugandan Ministry of Health guidelines (which recommends visits every 3 months) as this intervention will occur at the time of diagnosis rather than when a person is deemed “stable” in care. Before the designated individual goes to clinic in any given month, they will be responsible for connecting with each group member to ask about how they are feeling and to see if they have any questions to ask of the HIV clinic staff. That individual will then attend HIV clinic and communicate about the status of each group member. They will collect useful information from the clinic and pre-packed ART for each group member. ART may be distributed in MEMS Cap bottles if these are available and if the participant is willing. These allow for transmission of the date and time of bottle opening to research staff only to better monitor medication adherence. The “Early CCLAD” group will then meet at their predetermined location so that the individual who attended clinic can share information from the clinic and can distribute the ART to each person in the group.

Anticipated annual health care visit schedule*:

- Month 1: ART start for group + comprehensive clinical exam + laboratory testing as needed
- Month 2: ART refill (in community)
- Month 3: ART refill (in community)
- Month 4: ART refill (in community)
- Month 5: ART refill (in community)
- Month 6: ART refill for group + clinical review + laboratory testing as indicated/needed
- Month 7: ART refill (in community)
- Month 8: ART refill (in community)
- Month 9: ART refill (in community)
- Month 10: ART refill (in community)

Month 11: ART refill (in community)

Month 12: ART refill for group + clinical review + laboratory testing as indicated/needed

*Alternatively, some groups may decide to rotate and have group members attend clinic in 6-month intervals but not necessarily with other group or with all the group members.

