Follow-up data collection: Early CCLAD group participants will be given components of the intake survey (i.e. to assess mental health screening, perceived stigma, and social support) again 6-months after they began participation in the intervention. Additionally, data will be collected to assess retention in group care, ART medication pick-up, and HIV clinic outcomes.

Sample size determination

From our routine HIV testing study conducted at Nakivale Health Center III in 2013 ([name] et al, JAIDS 2014), we found an HIV prevalence of 4.5%. With a current population of about 110,000 (<https://reliefweb.int/sites/reliefweb.int/files/resources/69449.pdf>), this means approximately 4,950 in Nakivale are living with HIV. As this is a pilot study, sample size determination is not applicable. However, to assess the feasibility and acceptability of this intervention, we aim to enroll approximately 70 individuals into the early community client-led ART delivery (early CCLAD) intervention. To reach this number, we plan to enroll 3,000-4,000 individuals to participate in the initial survey and HIV test.

Sampling method and procedures

We will invite all individuals newly diagnosed with HIV to participate in the intervention. There will be no randomization.

Outcomes and Variables to be measured in the study

Primary outcome:

- Linkage to HIV clinical care: attendance of one Early CCLAD group meeting within 90 days of study initiation

Secondary outcomes:

- Retention in care: Early CCLAD group meeting attendance each month
- ART medication pick-up
- Date and time ART medication bottle is opened (if the client is willing to use a MEMS Cap bottle which will record this information)
- HIV clinical outcomes (CD4, viral load, clinic visits outside required visits)
- Variables collected in the intake survey (and 6-month survey for those in Early CCLAD groups):
 1. Demographic information (i.e. refugee status, marital status)
 2. Non-communicable disease screening
 3. Migration patterns
 4. Perceived health
 5. HIV testing history
 6. HIV-related stigma
 7. Patient health questionnaire depression assessment (PHQ-9)
 8. Generalized anxiety disorder (GAD-7)
 9. Post-traumatic stress disorder (PCL-6)
 10. Social support (BS6)

Process outcomes:

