- Uptake/Acceptability: number offered Early CCLAD, number accepted Early CCLAD (and reason for not accepting for those unwilling to participate), number placed into an Early CCLAD group, number attending first Early CCLAD meeting, number retained in Early CCLAD meetings.
- Early CCLAD group characteristics: size, sex of group, age of group, country of origin of group, location of group meetings, time of group meetings, group leader characteristics, choice of whether or not/how to support individual attending clinic monthly, group connecting activity, the frequency of “up referral” and retention in group care for those referred to resume monthly clinic visits in person
- Assessing Early CCLAD group intervention feasibility and fidelity:
 1. Group size remains between 3-12
 2. First group meeting to include the following components:
 - Includes all team members
 - Occurs within 90 days of initial diagnosis for all team members
 - Is led by the clinic HIV RN
 - Plan made for future meetings dates/locations
 - Decision made about whether or not to support group member attending clinic each month and in what way to support them

- Specify the clinic attendance schedule for the next 6 months
- Choose whether or not to have a “connecting activity”
- Select a Team Leader
- Each individual to have a comprehensive clinical exam and any necessary laboratory testing
- 3. Monthly group responsibilities (to be checked each month):
 - A representative group member scheduled to attend clinic that month is to check in with each individual prior to going to clinic
 - A group representative attends HIV clinic and picks up ART for the group
- 4. Monthly group meeting to include the following components:
 - Meet as a group in the selected location at the predesignated time and distribute ART
 - i. Note: The Team Leader for each Early CCLAD group will be responsible for collecting and submitting the following information to the research team each month: Date of meeting (and was this the originally planned date, if not, why/how did it change)
 - ii. Time of meeting (and was this the planned time, if not, why/how did it change)
 - iii. Location of meeting (and was this the planned location, if not why/how did it change)
 - iv. Number of participants in attendance (record de-identified code for each participant in attendance)
 - v. Length of meeting (in minutes)
 - vi. Estimate of time spent discussing information from clinic (in minutes)

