The data will be reviewed at least twice monthly by the research team to ensure the validity and integrity of the data as well as adherence to the IRB-approved protocol. In addition, data will be reviewed no less frequently than monthly by the PI ([name]). If there are any deviations from the IRB-approved protocol, the PI will be notified immediately, and the study will be stopped. The research team will closely monitor the study to ensure the safety of subjects. The Head Research Assistant (i.e. Project Manager) will conduct safety reviews twice monthly at the study site. HIV counselors will attend periodic training sessions to assist them in their role and to ensure quality procedures are used when conducting rapid HIV tests. Study staff will use precautions when conducting HIV testing and all materials will be disposed of in a secure fashion using biohazard containers as is the protocol in Nakivale. Research assistants will receive specific training in data security and methods to ensure safety of subjects and they will be given information on proper expectations regarding reporting of adverse events. The study will be monitored closely for any breaches in confidentiality. In the event of any of the problems described above, the study staff will notify the PI ([name]) and she will intervene to correct the problem.

Data management and analysis

Data will be stored and reviewed in the web-based data storage platform (e.g. REDCap). Data analysis will be conducted in conjunction with a biostatistician at the University of Washington. All data shared with biostatisticians, or anyone outside of the immediate research team, will be deidentified prior to transfer.

Dissemination plan

During the study period, the Head Research Assistant and the PI will discuss the study with stakeholders at the clinic and will share regular feedback about the progress of the study. Upon study conclusion, the PI will meet with stakeholders to share the study findings. If the accepted, the results will also be presented at international conferences and published in a peer-reviewed journal.

Study laminations

Not applicable.

Ethical considerations

Risks and Discomforts: There is minimal anticipated discomfort due to finger prick for the HIV test. The surveys used for data collection will may cause distress, however, research staff can refer participants to non-research clinic staff for counselling as the need arises. While patients choosing to

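### Does the rule that any protocol deviation stops the study clash with the promise that the PI will correct problems?

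*Protocol*

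**What the plan says.** The Protocol, section 7, Quality control measures, describes data review at least twice a month by the team and at least monthly by the PI, and then sets the rule: "If there are any deviations from the IRB-approved protocol, the PI will be notified immediately, and the study will be stopped". After sentences on safety reviews, training and confidentiality, the paragraph ends with a general response: "In the event of any of the problems described above, the study staff will notify the PI", and "she will intervene to correct the problem".

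Two other parts of section 7 bear on what might count as a deviation.

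- **90-day limit.** The description of the Early CCLAD intervention says "We will not initiate a participant into group after 90 days of diagnosis". The fidelity list under Process outcomes scores the first meeting on whether it "Occurs within 90 days of initial diagnosis for all team members".
- **Monthly meetings.** The text on monthly meetings says the "intervention will require monthly group meetings", and the secondary outcomes include "Retention in care: Early CCLAD group meeting attendance each month".

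The SAP is a single descriptive paragraph and says nothing about deviations, stopping or fidelity.

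**The concern.** The rule has no severity threshold. Taken literally, one misfiled consent form or one wrongly administered survey would halt the study, while the last sentence of the paragraph seems to ask only for correction. The text does not say whether stopping is a pause or an end, whether it covers enrolment, data collection or the groups themselves, or how the study restarts.

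The overlap with fidelity makes this look worse. A pilot of feasibility expects some shortfalls and counts them. If a late first meeting is both a scored outcome and a reason to stop, the study could be interrupted by the very events it set out to observe. If staff simply corrected problems and carried on, the study would depart from its approved wording. At stake would be uninterrupted accrual and follow-up on the first reading, and compliance and clear reporting on the second.

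**Working it through.** The documents give no figure for this point, so there is nothing to reproduce. The check is a reading of the passages, followed by an illustration with assumed rates.

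**1. The two sentences in Quality control measures.** The first is specific: a deviation leads to notification of the PI and a stop. The second is general: it covers the problems named in the paragraph, including safety and confidentiality, and leads to notification and correction. Doing both in sequence (notify, stop, correct) breaches neither. The sequence is only partly written out, because the place of correction and restart is not stated. The PI is both the person notified and the person who intervenes, so the question of who acts is partly answered.

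**2. Monthly meetings.** The requirement describes how the intervention is scheduled. The secondary outcome counts participants' attendance. The Protocol lets participants leave the groups at any time, so a missed meeting is participant behaviour that the design foresees. It is not in itself a departure by study staff, and this supposed overlap falls away.

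**3. The 90-day limit.** The prohibition binds staff. The fidelity item can be read as the check that they kept to it. Recording an event and also acting on it is not inconsistent. The Protocol does not say whether a late start triggers the stop, so this overlap remains, as a gap.

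**4. Departures the Protocol itself allows.** An individual first meeting with the clinician, regrouping to keep at least three members, rescheduled meetings and documented programme adaptations are all provided for. They are arguably not deviations, so much of the line between deviation and adaptation can be inferred.

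**5. How often the rule would be triggered.** Inputs from Sample size determination: "we plan to enroll 3,000-4,000 individuals to participate in the initial survey and HIV test", and about 70 participants in the intervention. The rate r per person is assumed, and events are taken as independent.

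Chance of at least one deviation = 1 − (1 − r)^n

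| Assumed rate r | n = 3,000 | n = 4,000 |
|---|---|---|
| 1 in 1,000 | 1 − 0.999^3000 = 95.0% | 1 − 0.999^4000 = 98.2% |
| 1 in 10,000 | 1 − 0.9999^3000 = 25.9% | 1 − 0.9999^4000 = 33.0% |
| 1 in 100,000 | 1 − 0.99999^3000 = 3.0% | 1 − 0.99999^4000 = 3.9% |

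The rate at which the chance reaches 50% is 1 − 0.5^(1/n): 0.000231 (1 in 4,329) for n = 3,000 and 0.000173 (1 in 5,771) for n = 4,000.

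For the 90-day limit alone, n = 70: 1 − 0.999^70 = 6.8% if 0.1% of starts are late, and 1 − 0.99^70 = 50.5% if 1% are.

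At a fixed average rate, clustering of errors by site or staff member lowers all these figures. They measure the chance that a literal rule is triggered once, not any harm to the results.

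**6. Effect on the analysis.** The Protocol says a sample size calculation does not apply, and the SAP reports counts, proportions and numbers of visits. No stated error rate or power depends on the rule. Team Leaders also report each meeting's date, whether it was the planned date and, if not, why it moved. A pause that disrupted meetings should therefore be visible in the process data.

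**The case for a change.** The best case for acting is that stop-then-correct settles only the apparent conflict. Duration, scope and restart are still undefined, in a rule that is explicit and unqualified. Scope has practical weight, because the group meeting is where ART is handed out; whether a stop reaches the meetings should not be left to inference. The remedy would also be cheap: one amended paragraph, or one in the report if conduct is over.

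Part of this stands. The detail is missing, and no passage says how a breach of the 90-day limit is to be treated. But it is a matter of conduct and reporting. Participants may attend the clinic in person whenever they need to, so the groups are not their only contact with care. Limiting the stop to serious deviations would replace a cautious rule in an ethics submission with a preferred one, and would require a definition of seriousness that the documents do not supply. Whether the ethics committee's policy or site procedures already define deviation, suspension and restart cannot be seen from these documents.

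The cheap amendment is also probably too late. The Protocol planned data collection through 2021, and the SAP of 31 March 2023 describes finished work.

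**Conclusion.** The concern identifies an ambiguity, not a contradiction, and it does not call for a change to the plan. The natural reading is that the study pauses, the PI corrects the problem and work resumes; on that reading the feasibility and acceptability results are sound. If staff in fact corrected problems without pausing, process data would still have been collected, and the cost would be to compliance and clear reporting. Saying in the report which deviations occurred and how the rule was applied is ordinary good practice and needs no new analysis.

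The size cannot be fixed. The chance of at least one trigger over 3,000 to 4,000 encounters spans 3.0% to 98.2% across the assumed rates, so the documents do not support calling a trigger likely or unlikely.

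The conclusion rests on two assumptions: that stopping meant a pause, and that departures the Protocol provides for were not treated as deviations. A final termination after a minor error would be a different matter, but the promise to correct points away from that reading.

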STATISTICAL ANALYSIS PLAN

Study Title: Early Community Client-Led ART Delivery (CCLAD) to Optimize HIV Care Engagement in Nakivale Refugee Settlement

Document Date: 31 March 2023

NCT04736316

STATISTICAL ANALYSIS PLAN

Counts and frequencies were reported for demographic characteristics, mental health conditions (depression, anxiety, PTSD), self-reported health status, and social support for the overall sample and were stratified by Early CCLAD participation. Among Early CCLAD participants, the proportions of those who initiated ART, and the proportion who became virally suppressed were documented. Additionally, among Early CCLAD participants, the number of visits with Early CCLAD groups and HIV clinic visits were recorded.

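### The SAP specifies no analysis of the protocol's only primary outcome, does not tabulate the uptake cascade, and leaves its populations undefined

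*SAP*

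**What the plan says.** Protocol, section 7, Outcomes and Variables, lists a single primary outcome: "Linkage to HIV clinical care: attendance of one Early CCLAD group meeting within 90 days of study initiation". It states no denominator.

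The Process outcomes list that follows sets out uptake and acceptability as a cascade: "number offered Early CCLAD, number accepted Early CCLAD (and reason for not accepting for those unwilling to participate"), then "number placed into an Early CCLAD group, number attending first Early CCLAD meeting, number retained in Early CCLAD meetings". The fidelity items for the first group meeting include "Occurs within 90 days of initial diagnosis for all team members". For each monthly meeting the Team Leader is to submit the date and "record de-identified code for each participant in attendance".

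The protocol's Data management and analysis section gives no method or analysis population. It says only that a biostatistician will be involved.

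The SAP, dated 31 March 2023, has three elements:

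- Baseline counts and frequencies "for the overall sample and were stratified by Early CCLAD participation".
- Care outcomes: "Among Early CCLAD participants, the proportions of those who initiated ART, and the proportion who became virally suppressed were documented".
- Visits: "Additionally, among Early CCLAD participants, the number of visits with Early CCLAD groups and HIV clinic visits were recorded".

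**The concern.** A plan that names one primary outcome should say how that outcome will be summarised. This SAP mentions neither linkage, nor a 90-day window, nor a primary outcome, and it lists none of the cascade steps. Both of its populations are undefined.

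Three things are at stake. First, the protocol's hypothesis (Ethical considerations, Potential Benefits) concerns how many people become linked to treatment, and no specified analysis answers it. Second, the stated aim is feasibility and acceptability. Acceptance among those offered a group is one of the protocol's listed acceptability measures, and a reader of the SAP outputs may be unable to recover it. Third, with no stated denominator, the same attendance data could be reported as quite different percentages.

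**Working it through.** **Step 1. Match each protocol item to the SAP.**

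| Protocol item | In the SAP? |
|---|---|
| Proportion attending at least one group meeting | No; only a number of group visits among participants |
| Within 90 days | No window stated |
| Denominator for linkage | None (none in the protocol either) |
| Offered, accepted, reasons for refusal | No |
| Placed, attended first meeting, retained | No; visit counts bear on attendance only |
| ART start, viral suppression | Yes, among participants |

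**Step 2. How close do the visit counts come?** A count of one or more group visits shows that a meeting was attended. Timing is partly covered elsewhere: the protocol's description of the intervention bars entry to a group later than 90 days after diagnosis. Absent deviations, most first meetings should therefore fall in the window. The counts approximate the numerator, but the timing is assumed rather than checked and no proportion is formed.

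**Step 3. What is a participant?** The protocol pays each participant who attends the first meeting and speaks of participants assigned to a group. Both usages suggest that a person becomes a participant on acceptance or placement, before attending. The SAP does not say so. If it meant people who had attended a meeting, attending one meeting would be 100% by construction.

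**Step 4. What is the overall sample?** Consent and the intake survey come before the HIV test, so the surveyed sample includes people who can never be offered a group. If the overall sample is everyone tested, splitting it by participation gives 70/4,000 = 1.75% to 70/3,000 = 2.33%, which is not uptake among those offered. If it is the newly diagnosed, the split does give overall uptake, but none of the intermediate steps.

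**Step 5. Day 0.** The primary outcome counts from study initiation; the group-entry limit and the fidelity item count from diagnosis. Under the described route of consent, survey and then test, enrolment and diagnosis nearly coincide. The wording still differs.

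**Step 6. Can the denominator matter?** The protocol's own derived figure reproduces: 0.045 × 110,000 = 4,950. The target of about 70 has no stated derivation.

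Inputs: target 70 and 3,000 to 4,000 tested (Sample size determination). Assumption A: 4.5% of those tested are newly diagnosed and offered a group. That figure is a 2013 prevalence from one site, not a yield of new diagnoses, and previously diagnosed people would lower it. Assumption B: 70 accept, and either 70 or 56 attend in time; the 56 is arbitrary.

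Offered under A: 0.045 × 3,000 = 135; 0.045 × 4,000 = 180.

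Exact (Clopper-Pearson) limits for x of n: the lower is the 0.025 quantile of Beta(x, n − x + 1) and the upper is the 0.975 quantile of Beta(x + 1, n − x). The upper limit is 1 when x = n.

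| Attend in time | Of 70 accepting | Of 135 offered | Of 180 offered |
|---|---|---|---|
| 70 | 100% (94.9 to 100) | 51.9% (43.1 to 60.5) | 38.9% (31.7 to 46.4) |
| 56 | 80.0% (68.7 to 88.6) | 41.5% (33.1 to 50.3) | 31.1% (24.4 to 38.4) |

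At the other extreme, if only 70 people are offered a group and all accept, the two denominators are the same. With all 70 attending in time, the all-offered figure therefore runs from about 39% to 100%, depending wholly on an assumption.

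**The case against.** The strongest reply is that this is a small, non-randomised feasibility pilot for which the protocol calls sample size determination not applicable, so description is enough. That stands against any demand for a hypothesis test, and none is made here. It does not excuse leaving the primary outcome out of the description.

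A second reply is that visit counts plus the 90-day limit on group entry nearly give the numerator. This is largely right, and the gap should not be overstated. What remains missing is the proportion, the denominator and an explicit check of timing.

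A third reply is that choosing all those offered as denominator is a preference. The protocol states none, and its eligibility criteria include willingness to join a group, so those who accepted are a defensible population. This stands, and is why both should be shown. The SAP is also written in the past tense and dated after the planned end of data collection in 2021, so a denominator chosen now may be post hoc and should be disclosed as such.

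Three stronger readings are tempting but unsupported:

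- A reader might infer that the window could run to day 180 after diagnosis, because people diagnosed within the last 90 days are eligible and the outcome counts a further 90. The bar on group entry after 90 days from diagnosis, and the consent-then-test route, do not support that.
- A reader might infer that ART start and suppression are presented without saying they are conditional on joining. The SAP states the condition; only the term participant is undefined.
- A reader might set the illustrative percentages against the historical 54% linkage. The SAP plans no such comparison.

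**Conclusion.** The concern holds. The SAP omits any analysis of the only primary outcome and does not tabulate the uptake cascade, and the protocol's analysis section does not fill the gap. This rests on reading the two documents together and needs no assumption. The missing primary analysis must be fixed; the population definitions and day 0 are clarifications that the analysis needs in order to be unambiguous.

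The numerical effect in this trial is unknown. The 39% to 100% range depends on the assumed 4.5% yield and on all 70 attending in time. It shows that the denominator can matter, not that it did.

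**What to change.** 1. Add the primary analysis: the number and proportion attending at least one group meeting within 90 days, with an exact 95% CI, among all consenting newly diagnosed people offered Early CCLAD. Show the same proportion among those who accepted beside it.
2. Tabulate the counts offered, accepted, placed, attending the first meeting and retained, with reasons for refusal.
3. Define Early CCLAD participant (accepted, placed or attended) and overall sample (everyone tested or the newly diagnosed).
4. Reconcile study initiation with diagnosis as day 0 of the 90 days.
5. State that the denominators and the interval were added after the 2019 protocol, with the date and whether data were already available.

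The cost is SAP wording and a little more table work. The protocol already plans the cascade counts, meeting dates and attendance codes, so no new data collection is asked for. The all-offered percentage cannot exceed the percentage among acceptors and may be lower, so the headline result may look less favourable.
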